## STUDY OVERVIEW

This pilot study will test the appeal and toxicity of e-cigarettes as a substitute for cigarettes among smokers with aerodigestive tract cancers or bladder cancer. Participants will receive e- cigarettes for 9 weeks and be asked to substitute the e-cigarette product for their usual combustible product. Primary outcomes include e-cigarette appeal, e-cigarette use/satisfaction and combustible tobacco toxicity.

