## STUDY TIMELINE AND FOLLOW-UP

The trial is designed to allow for patient visits every 3 weeks for 12 weeks. The coordinators will work with the participant and the participants' medical care teams to schedule and conduct the visits. We will contact enrolled subjects for follow-up at 6 and 12 months after enrollment. Each time, we will attempt to contact the subjects 3 times by phone over a period of 3 weeks. During the call the subject will be asked if they are still using an e-cigarette, what brand they are using, what concentration of nicotine they use, how many times a day they use it, and how often they currently smoking any combustible tobacco products.

Participants will receive free e-cigarette products for the first 9 weeks of the trial and \$20 for each visit (\$100 total). Participants that travel more than 20 miles one-way for a study-only visit (no other appointments scheduled on the day of their study visit) will be given a \$10 gas card.

Time	Baseline	3 weeks	6 weeks	9 weeks	12 weeks
Activity	Consent; survey; ecig instruction; urine; CO	Survey; ecig refill; urine; CO	Survey; ecig refill; CO	Survey; qualitative interview; urine; CO	Survey; CO
Compensation	\$20	\$20	\$20	\$20	\$20

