## OUTCOMES ASSESSMENT

Each visit will include a checklist that assesses how the participant is using the e-cigarettes and what problems he/she may be encountering with the use of the e-cigarette device. Adverse events will be assessed with a checklist for commonly occurring side effects from e-cigarettes and nicotine products. The coordinators will conduct and audio-record a 10-15 minute qualitative interview at 9 weeks soliciting perceptions about e-cigarettes to be transcribed and analyzed for common themes that could be useful in developing the larger intervention.

*Behavioral assessments:* We will use a Timeline Follow-Back Questionnaire (TLFB) to document use of cigarettes at baseline and cigarettes/e-cigarettes at baseline, 3, 6, 9, and 12 weeks. At follow up visits participants will be instructed to bring in all used and unused e- cigarettes, in order to verify reports of e-cigarette use. We will evaluate appeal with attitudinal ratings, on a 5-point Likert-type scale, e-cigarette ease of use, satisfaction, and enjoyment, and willingness to continue to purchase e-cigarettes in the future. All questionnaires are being programmed using a secure web-based system set up and maintained by the Dartmouth Bioinformatics group led by [name].

*Biomarkers of behavior:* Cigarette smoking will also be measured with exhaled carbon dioxide. We will assess expired breath CO2 using Micro Smokerlyzer meters (Bedfont Scientific), which have already been purchased for a previous study. The protocol will follow operating instructions that come with the devices, and the devices will be calibrated weekly with 40PPM CO2/air mixture. E-cigarette smoking will be measured with urine propylene glycol, the main constituent of e-cigarette aerosol. Some 40% of ingested

propylene glycol is excreted unchanged in the urine.

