### Qualitative Analysis

A follow up interview will be conducted at week 9. The interview will be transcribed and a thematic analysis will be conducted to evaluate common issues encountered by smokers with cancer patients who use e-cigarettes. Thematic analysis consists of examination of text by identifying and grouping themes, followed by coding, classifying, and developing categories. Transcripts are uploaded into a qualitative analytic software program and analyzed using Atlas.ti, a qualitative coding program. Co-investigator [name] has experience using similar qualitative methods to interview health professionals. She will supervise the coders, staff at the Centers for Health and Aging at Dartmouth who have been trained to perform similar analyses in other studies.

*Substitution assessment:* The proportion of participants who report use of e-cigarettes during each follow-up visit during treatment will also be computed (along with a 95% confidence interval). This proportion is expected to be at least 0.5. With 40 participants, width of a 95% confidence interval around this proportion will be at most 0.32. The satisfaction with e- cigarettes (averaged across 3 treatment assessments) will be summarized among participants using descriptive statistics and the amount of e-cigarette product returned at each follow-up period will be summarized across the treatment period.

To explicitly test the substitution/replacement mechanism of e-cigarettes, we will perform an exploratory parallel process growth model fit within a structural equation modeling framework. In this model the trajectory over time of both frequency/quantity of cigarette use and frequency/quantity of e-cigarette use will be modeled assuming individual-level latent intercept and slope (i.e., latent growth curve model). A significant negative association between the latent slope of e-cigarettes and the latent slope of combustible cigarettes would be consistent with the replacement/substitution hypothesis. The model provides an explicit statistical test of the hypothesis that, as e-cigarette usage increases, combustible cigarette usage decreases. Power for this analysis is computed as that for an individual-level correlation coefficient assuming 40 participants. There will be at least 80% power to detect a correlation that is at least -0.4 between these two individual-level slopes. Figure 7 shows a diagram of the parallel process growth model.

n

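### The substitution correlation probably pairs two self-reports from participants asked to substitute, and no planned analysis checks it against breath CO or product consumed

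*Combined protocol and SAP*

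**What the plan says.** All references are to the combined protocol and SAP.

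- **The model.** The Substitution assessment paragraph (printed under Qualitative Analysis) plans a parallel process growth model: "In this model the trajectory over time of both frequency/quantity of cigarette use and frequency/quantity of e-cigarette use will be modeled". A significant negative association between the two latent slopes is to be read as consistent with substitution. The paragraph calls the model exploratory. However, H1 predicts the negative slope correlation, and the Primary outcomes list includes the correlation between the two changes.
- **The measure of use.** Outcomes Assessment uses a Timeline Follow-Back Questionnaire (TLFB) "to document use of cigarettes at baseline and cigarettes/e-cigarettes at baseline, 3, 6, 9, and 12 weeks". No other frequency/quantity instrument covering both products is described.
- **The instruction.** Under Study Overview, participants will "be asked to substitute the e-cigarette product for their usual combustible product". Under Study Design they are also told that the product should in theory be less harmful than smoking.
- **Returned product.** Participants bring back used and unused product "in order to verify reports of e-cigarette use". In the analysis section, "the amount of e-cigarette product returned at each follow-up period will be summarized across the treatment period". There is no rule for a report and a count that disagree.
- **Breath CO.** The visit table lists CO at all five visits, for example "Survey; ecig refill; urine; CO" at week 3 and "Survey; ecig refill; CO" at week 6. Outcomes Assessment treats exhaled gas as a measure of smoking (the text writes CO2 in places; I read it as CO). Its planned analyses are a paired t-test and a mixed model under Toxicity Assessment, neither linked to e-cigarette slopes.

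**The concern.** If both series are TLFB reports, each participant answers about both products on the same questionnaire after being asked to replace one with the other. A participant inclined to please would report more e-cigarettes and fewer cigarettes than actually used. The two errors then move in opposite directions within a person, which is the pattern the model takes as a sign of substitution.

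At stake is how a component of H1 is read. The paragraph describes the model as an explicit test that cigarette use falls as e-cigarette use rises. On self-report alone, a negative slope correlation could reflect behaviour, reporting, or both. The CO analyses under Toxicity Assessment show whether CO falls on average. They do not show whether the participants who took up e-cigarettes are those whose smoke exposure fell.

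**Working it through.** **1. The plan's own figure.** Inputs from Substitution assessment: n = 40, correlation -0.4, power at least 80%. Alpha and sidedness are not stated for this test; the toxicity t-tests use 0.05 two-sided.

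Fisher z: power = Phi(sqrt(n - 3) x atanh(0.4) - z_alpha), where sqrt(37) x atanh(0.4) = 6.083 x 0.4236 = 2.577.

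- One-sided 0.05: Phi(2.577 - 1.645) = 82.4% (simulated t-test about 83%).
- Two-sided 0.05: Phi(2.577 - 1.960) = 73.1% (simulated about 74%).

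The stated power is therefore met only by a one-sided test. That is a separate matter, but it affects the nominal rate below.

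**2. What shared reporting bias does.** Let z1 and z2 be independent true slopes with unit variance. Let b be a person-specific reporting shift, independent of both, with variance f.

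- Reported e-cigarette slope: e = sqrt(1 - f) z1 + b
- Reported cigarette slope: c = sqrt(1 - f) z2 - b

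Each has variance (1 - f) + f = 1, and Cov(e, c) = -Var(b) = -f. The expected correlation is -f although the true slopes are unrelated. The value of f is assumed; the documents give none. Like the plan's power statement, this treats the test as one of a simple correlation.

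Chance of a significant negative correlation at n = 40 (simulated):

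| Assumed f | Expected r | Two-sided 0.05, negative side | One-sided 0.05 |
|---|---|---|---|
| 0% | 0 | 2.5% | 5% |
| 10% | -0.1 | 9% | 15% |
| 20% | -0.2 | 24% | 35% |
| 30% | -0.3 | 47% | 60% |
| 40% | -0.4 | 74% | 83% |

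At f = 40% the bias alone gives the correlation for which the plan is powered.

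**3. Conditions on the bias.** A shift constant from baseline goes into the intercepts. A shift equal in everyone changes only the mean slopes. The bias must both vary between people and change over time.

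A change after baseline is plausible: product and instruction come at enrolment, and e-cigarette use in the prior 30 days is an exclusion. The shift need not keep growing. For visits at 0, 3, 6 and 9 weeks (mean 4.5, sum of squared deviations 45), a step of size 1 from week 3 onward gives a least-squares slope of (-1.5 + 1.5 + 4.5)/45 = 0.1 per week.

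A visit-level simulation used these four visits and a step shift. Its assumptions were independent true 9-week changes with SD 5 per day, visit noise with SD 2 and a mean shift of 3:

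| SD of shift between people | Mean r | Significant negative (two-sided 0.05) |
|---|---|---|
| 0 | 0.00 | 2% |
| 2 | -0.09 | 8% |
| 3 | -0.18 | 21% |
| 4 | -0.28 | 45% |
| 5 | -0.38 | 71% |

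**4. What CO would do.** Replace c by a CO slope that does not depend on b. When the true slopes are unrelated, its covariance with e is zero whatever f is, so the false-positive rate returns to about 2.5% at every f. This assumes that a wish to please does not alter the CO reading.

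**The case against.** Several points on the other side have force.

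- **The data source is not stated.** A reader might infer that the plan commits both series to self-report. It does not. TLFB input is a strong inference for cigarettes and a likely one for e-cigarettes. E-cigarette quantity could rest on product counts, since amount used per week is among the primary outcomes. The model diagram is not visible in the text available. This stands, and limits the claim.
- **The reports are not unchecked.** Returned product is meant to verify e-cigarette reports, urine propylene glycol is named as a marker of e-cigarette use, and CO and NNAL are tested under H2. If smoking fell only on paper, mean CO would not be expected to fall. This stands for mean levels. It does not reach the slope correlation, and no rule says how returned product changes a report.
- **The bias is hypothetical.** Its size is assumed, the equal share in both slopes is a simplification, and f = 40% was chosen to match -0.4. The trial is presented as one of appeal in smokers unwilling to quit, not of cessation, which may soften the pressure to please. All of this stands; the table shows sensitivity and does not predict a result.
- **The model is exploratory, in a pilot of 40.** This lowers the stakes. It does not remove them, because the correlation is also an H1 prediction and a listed primary outcome.

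**Conclusion.** The concern holds in a limited form. As far as the text shows, the substitution correlation probably rests on two self-reports from the same questionnaire, and nothing planned checks that correlation against an objective series. If reporting bias arises after enrolment and varies between participants, it induces a negative correlation with no true substitution. For an assumed share of 10% to 40% of each slope's variance, a significant negative result appears in about 9% to 74% of trials (two-sided 0.05, n = 40).

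A reader might infer that a negative correlation would be no evidence of behaviour change. The documents do not support that: they give no size for the bias, they include some verification, and they describe the finding only as consistent with substitution. Possible bias weakens this evidence without cancelling it. The point is a cheap improvement, not a fault that invalidates the analysis.

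**What to change.** In Substitution assessment:

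1. Name the source of each series in the growth model, and state how returned product is used when it disagrees with a report.
2. Pre-specify a sensitivity version with breath CO as the combustible series, fitted against (a) reported e-cigarette use and (b) product consumed, that is dispensed minus returned, over weeks 0 to 9 only.
3. Report the slope correlation and its confidence interval from every version. Describe the self-report result as supported by objective data only if the confidence interval of the CO-based correlation also lies below zero. Otherwise report it as not confirmed, which is not the same as refuted.

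Agreement in sign alone would be too weak a criterion. In a simulation with unrelated true slopes and a bias-free objective version (assumed slope reliability 0.25 to 1.0), a significant self-report result plus the same objective sign still gave false claims in 27% to 38% of trials at f = 30% and 40% to 47% at f = 40%.

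**Cost.** The work is additional model fits on data the plan already collects, plus a common unit for product consumed, because participants may use tank liquid or prefilled cartomizers at different strengths. The drawback is precision. Product is supplied at enrolment and refilled at weeks 3 and 6, so it gives only three intervals and no week-12 value. CO is also noisier than reported cigarettes. If the CO slope had a reliability of 0.25 (assumed), a true correlation of -0.4 would appear as -0.4 x sqrt(0.25) = -0.2, which the table above shows is detected in about 24% of trials.

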### Primary outcomes:

**Appeal (H1)**—E-cigarette use and amount of e-cigarette product used per week, proportion of participants that report e-cigarette use at each assessment, satisfaction scores for e-cigarettes, and whether they continue e-cigarette use at 12 weeks (3w after end of trial). Correlation between change in e-cigarette use and change in cigarette use.

Combustible Tobacco Toxicity (H2)—Exhaled CO, urine NNAL and 1-hydroxy naphthaline (1- HOP). Because smokers are good at regulating nicotine intake, we expect no change in urine cotinine over time.

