and are being embraced by some public health programs, they are not free from toxicity. Because of the lack of regulation of these products, we are now faced with an array of products, and no standardization of nicotine concentration, flavoring, and contaminant allowance. Lipoid pneumonia has been reported in one e-cigarette user, probably as a result of flavoring oils or oil contaminated glycerol. Use of high voltage batteries in refillable tank devices converts propylene glycol at very high temperatures to formaldehyde, but not to the levels found in tobacco smoke. Data are starting to appear that suggest that some of the flavor components of e-cigarettes may affect lung epithelial cells and inflammation, and even nonflavored vapor affected macrophage-moderated inflammation in mice exposed to the vapor. Thus, the sum of the limited data available so far suggests that, compared to cigarette smoke, e-cigarette vapor exposes users to much lower levels of toxins. While it remains unknown what the impact on health or oncological outcomes of e-cigarettes may be, the factors outlined above suggest a clear theoretical safety advantage over continued use of combustible tobacco products for patients with cancer. Given almost universal access to these products and the fact that cancer patients are using them, we have an obligation to determine how they affect consumption of combustible tobacco and whether their use affects intermediate medical outcomes. That is the overarching purpose of the present research.

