### E-CIGARETTE REGULATION: IMPLICATIONS ON STUDY DESIGN

As detailed below, the specific aims of this project are to determine the appeal and toxicity of e-cigarettes in current smokers with a smoking-related cancer. This is NOT a smoking cessation study; instead, it examines changes in intake for two tobacco products when administered together. There is a regulatory basis for the decision to focus on appeal and toxicity, and not smoking cessation. When e-cigarette devices first attempted to enter the US market, the Food and Drug Administration (FDA) blocked shipments on the basis that e-cigarettes were unapproved drug delivery devices and must first pass through FDA's New Drug Application process before they could be legally sold. E-cigarette manufacturers sued, arguing that e-cigarettes contained nicotine derived from tobacco and were therefore a tobacco product; the US Court of Appeals (Washington DC) ruled in their favor; and the FDA decided not to seek further review. The FDA then determined that they would "deem" e-cigarettes to be covered under the *Family Smoking Prevention and Tobacco Control Act* (deeming is in process at this date). In the meantime, the FDA has determined that any evaluation of the e-cigarette product for a therapeutic endpoint (such as treating nicotine addiction) requires an Investigational New Drug Application (involving animal pharmacology and toxicity studies, manufacturing information on the product, etc.). This regulation does not allow scientists not closely affiliated with an

e-cigarette company to study these products as therapeutic devices. Moreover, e-cigarette companies have made it clear in US courts that they do not seek approval as a drug delivery device.

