**Toxicity Assessment:** Our measures of toxicity, urine NNAL, 1-HOP and CO2 will be compared between the baseline and 9-week assessments via paired t-test. For NNAL, assuming a standard deviation of change in this measure of 3.8 pmol/mg creatinine (as was seen in Joseph et al. 2008), with 40 participants, this test will have 80% power at the two-sided 0.05 significance level to detect a change from baseline of 1.7 pmol/mg creatinine. There is not enough information available on 1-HOP to perform a test of power, so analysis of this metabolite is considered exploratory. For expired CO, assuming a standard deviation of change in this measure of 17.0 ppm, with 40 participants, a paired t-test comparing baseline to 9-week will have 80% power at the two-sided 0.05 significance level to detect a change from baseline that is 7.7 ppm. Additionally, since CO2 will be measured several times throughout the treatment period, the trajectory of change over time in this measure will be modeled via linear mixed effects models including random intercept and slope terms to account for repeated observations within individual. With repeated measurements of CO, the power for the mixed model will be greater than that of the paired t-test of change from baseline to detect this change over time.

We will also evaluate toxicity by analyzing cotinine level to assure that the adverse effect of increased cotinine (resultant from increased e-cigarette usage without similar decrease in combustible cigarettes). To do this, we will compute the number of participants with an increase in cotinine over the course of the study and consider this an adverse event. With 40 participants, confidence intervals around this adverse event percentage will be at most 0.32 percentage points. The table below gives the probability of observing at least 1 participant with an increase in cotinine given different true percentage of participants with this adverse event. For example, if the population-wide true percentage of participants with cotinine increase is 0.5%, then the probability of observing at least 1 of the 40 study participants with an increase is 0.18.

True percentage of participants with increase cotinine	Probability of observing at least 1 adverse event (increase in cotinine)
0.5%	0.18
1%	0.33
2%	0.55
5%	0.87
10%	0.99

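### The slope correlation used to test substitution ignores the mean change in smoking, and no mean change in cigarettes is named or reported beside it

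*Combined protocol and SAP*

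**What the plan says.** The Substitution assessment (Statistical Analysis and Power Considerations) fits an exploratory growth model with a latent intercept and slope per participant for both e-cigarette and cigarette use. Its criterion is: "A significant negative association between the latent slope of e-cigarettes and the latent slope of combustible cigarettes would be consistent with the replacement/substitution hypothesis". Soon after comes the stronger sentence: "The model provides an explicit statistical test of the hypothesis that, as e-cigarette usage increases, combustible cigarette usage decreases".

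Hypothesis 1 predicts a significant negative correlation of growth slopes. The primary outcomes list, as their only item on cigarettes smoked: "Correlation between change in e-cigarette use and change in cigarette use".

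On purpose, the Toxicology section says "we have an obligation to determine how they affect consumption of combustible tobacco and whether their use affects intermediate medical outcomes". The section on e-cigarette regulation says of the study that "it examines changes in intake for two tobacco products when administered together".

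Cigarette use is recorded by Timeline Follow-Back (TLFB) at baseline and weeks 3, 6, 9 and 12 (Outcomes Assessment). The mean-change tests in the Toxicity Assessment are for NNAL, 1-HOP and the breath measure. None is described for cigarettes smoked.

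**The concern.** A correlation between slopes answers a relative question: do participants who take up e-cigarettes faster cut cigarettes more than participants who take them up slowly? The quoted sentence reads more naturally as an absolute claim that smoking goes down as e-cigarette use goes up.

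The two can separate in either direction. The correlation can be strongly negative while average smoking is flat or rising, because those who take up the product cut down and the others smoke more. It can be near zero when people cut down to a degree unrelated to their uptake. That would be a good result for the product, yet on the stated criterion it gives no support for substitution.

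Mean change in cigarettes smoked is a basic result to carry from this pilot into the larger randomized trial it is meant to prepare. The plan leaves that quantity, and its summary, to be chosen after the data are seen.

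**Working it through.** **Inputs.** From the Substitution assessment: n = 40 ("Power for this analysis is computed as that for an individual-level correlation coefficient assuming 40 participants") and r = -0.4 ("There will be at least 80% power to detect a correlation that is at least -0.4 between these two individual-level slopes"). Neither alpha nor sidedness is stated for this test. I assume 0.05 and try both; the plan's paired t-tests are two-sided ("80% power at the two-sided 0.05 significance level to detect a change from baseline of 1.7 pmol/mg creatinine").

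**1. The plan's power figure.** By Fisher's z, power = Φ(atanh(0.4) × √(40 − 3) − z), where atanh(0.4) × √37 = 0.4236 × 6.083 = 2.577.
- One-sided 0.05: Φ(2.577 − 1.645) = 0.824. The stated 80% is reproduced.
- Two-sided 0.05: Φ(2.577 − 1.960) = 0.731. It is not.

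Sidedness should therefore be stated, but that is a side matter. What counts here is that the formula has no term for the mean cigarette slope.

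**2. Why the mean drops out.** Let E and C be a participant's e-cigarette and cigarette slopes. For any constant k, Cov(E, C + k) = Cov(E, C) and Var(C + k) = Var(C), so corr(E, C + k) = corr(E, C). In a latent growth model the shift moves only the mean-slope parameter; the slope covariance is a separate parameter.

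**3. Size at the plan's design point.** Simulation of 100,000 trials per row, n = 40, bivariate normal slopes observed without error, mean cigarette slope in units of its between-person SD:

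| True r | Mean cigarette slope | Significant negative correlation, two-sided 0.05 | Same, one-sided 0.05 | t-test on mean slope shows a fall, two-sided 0.05 |
|---|---|---|---|---|
| -0.4 | -1 SD | 0.742 | 0.834 | 1.000 |
| -0.4 | -0.5 SD | 0.744 | 0.834 | 0.870 |
| -0.4 | 0 | 0.741 | 0.834 | 0.025 |
| -0.4 | +0.5 SD | 0.743 | 0.835 | 0.000 |
| 0 | -0.5 SD | 0.026 | 0.051 | 0.869 |

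The first four rows agree within simulation error. The simulated 0.74 differs slightly from 0.731 because the simulation uses the t-test for a correlation and the formula uses Fisher's approximation. With r = -0.6 the two-sided rate is 0.989 at all four means, so the pattern does not hinge on -0.4. The 0.026 in the last row is simply the one-directional error rate of the test.

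**4. What the missing estimate would offer.** For mean change with 40 complete pairs, the 95% CI half-width is t(39, 0.975) × SD/√40 = 2.023 × SD/6.325 = 0.320 SD. The change detectable with 80% power (two-sided 0.05) is 0.454 SD. The documents give no SD of change for cigarettes per day. An assumed range of 6 to 10 gives half-widths of 0.320 × 6 = 1.9 to 0.320 × 10 = 3.2 cigarettes/day, and detectable changes of 0.454 × 6 = 2.7 to 0.454 × 10 = 4.5 cigarettes/day.

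**The case against.** A reader might infer that nothing in the plan estimates change in smoking. The documents do not support that. The growth model includes a latent cigarette slope, and fitting it would normally yield the mean of that slope. The breath measure is described as a measure of smoking; Hypothesis 2 predicts that it and NNAL will fall, and both are tested by paired t-test, with a mixed model over visits for the breath measure. The count of participants whose cotinine rises is also presented as a check on added e-cigarette use without a matching cut in cigarettes. If smoking stayed flat, some of these results should show it.

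A reader might also infer that the plan would declare substitution while smoking had not fallen. That is too strong. The model is labelled exploratory, a negative association is said only to be consistent with substitution, and no decision rule is attached. The Abstract gives appeal as the overarching aim, and this is a single-arm pilot that is expressly not a cessation study. Figure 7, the model diagram, could not be read in the text available, so whether it marks mean slopes is unknown.

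These points limit the concern without removing it. A mean slope that is not named or reported does not bear on the conclusion. The biomarkers are indirect, sit under toxicity, and are not linked to the substitution reading. The exploratory label sits beside a claim of an explicit test, a numbered hypothesis and a primary-outcome entry.

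**Conclusion.** The point holds in limited form. The only stated criterion for substitution does not depend on mean change in smoking. At the plan's r = -0.4 and n = 40 it is met in about 74% of trials (two-sided 0.05; about 83% one-sided) whether average smoking falls, stays flat or rises. It is met in about 2.6% when smoking falls by half an SD on average with uncorrelated slopes, a fall that a test of the mean would detect in about 87%.

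The invariance is algebra and needs no assumptions. The percentages assume normal slopes measured without error and 40 complete participants. Measurement error in the slopes or dropout would change the rates, but would not make the correlation informative about the mean.

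Severity: should fix. The gap is an unnamed, unreported estimate and one overstated sentence. It is not an absence of any information on smoking.

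**What to change.** 1. In Hypothesis 1, the primary outcomes and the Substitution assessment, prespecify the mean change in TLFB cigarettes per day from baseline to week 9, with a 95% CI. A paired difference or a mixed model on weeks 0, 3, 6 and 9 would serve; naming the mean latent cigarette slope is an alternative.
2. Report it beside the slope correlation, and treat a negative correlation as support for substitution only together with that estimate. Requiring the whole interval to lie below zero is a stricter option and a design choice; it is not needed to close the gap.
3. Reword the quoted sentence to say that the correlation tests whether participants with faster e-cigarette uptake reduce cigarettes more than others.

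The cost is wording and one added estimate from data already collected at every visit. In a single-arm study the estimate describes change; it does not show that e-cigarettes caused it, and the text should say so.
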